## 2.2.5. Medication Accountability

The study investigators or the study coordinator will document the amount of study drug dispensed from UPMC-IDS. The study drug accountability records will be maintained at UPMC-IDS throughout the course of the clinical trial.

#### 2.3 STUDY ASSESSMENT

The complete study assessment and procedures are outlined in Table 1.

Subjects will undergo study procedures and screening RHC to confirm that eligibility criteria have been met. The RHC procedure may be performed on a separate day. If a RHC has been completed within 12 months from enrollment, test results may be considered for baseline measurements.

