#### 2.3.1. Screening Procedures

The outpatient visits will take place in various outpatient clinics and/or procedural areas throughout the University of Pittsburgh Medical Center (UPMC) Presbyterian and UPMC Montefiore Hospitals. The screening procedures will take place over 2 days if screening RHC is needed. Subjects will be asked to fast a minimum of 8 hours prior to each visit. These screening procedures will determine eligibility for the study.

- Obtain written informed consent
- Complete history and physical examination to include body weight, height
- Vital signs that include: blood pressure (BP), pulse, respirations, and pulse oximetry
- Obtain waist measurement
- Review of concomitant medications
- NYHA functional class assessment
- 6 minute walk test (6MWT) and Borg scale
- MetHb level via co-oximetry (pre single dose and 30 minutes post single dose). Due
  to unknown reasons the co-oximeter device may not be able to read metHb levels. In
  that event, a blood sample will be collected to test metHb levels at approximately 3045 minutes after the 40mg dose.
- Blood samples: fasting glucose, comprehensive metabolic panel, hemoglobin A1C, fasting lipid profile, PT/PTT, complete blood count, platelet and differential, NT-proBNP. The total volume of blood drawn is approximately 1 ½ tablespoons (20 mL). If any of the above tests were done within 30 days before the screening visit, they may or may not be repeated for research purposes.
- Urine pregnancy test for women of childbearing potential
- Echocardiogram (if subject has had an echocardiogram within the past year we may not obtain during screening)
- Right heart catheterization (with optional micromanometry), research blood samples
  for plasma nitrite concentrations, red cell iron-nitrosyl-hemoglobin and platelet studies,
  and open label 40mg oral nitrite dosing with methemoglobin level. Research blood
  samples will be collected prior to taking the 40mg oral nitrite and approximately
  30-45 minutes post-dose.
- A RHC may be performed to determine the PH-HFpEF eligibility criteria. The RHC will be conducted at UPMC Presbyterian Hospital, 3rd FL Catheterization Laboratory. The RHC hemodynamic measurement parameters for PH-HFpEF eligibility are as follows: mPAP ≥ 25 mm Hg; PCWP ≥15 and TPG ≥ 12. If a RHC has been completed within 12 months from enrollment, test results may be considered for baseline measurements. The total volume of blood drawn is approximately 1 ¾ tablespoons

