#### 2.3.2. Baseline Procedures

After eligibility has been confirmed, the following procedures will take place in various outpatient clinics and/or procedural areas throughout the University of Pittsburgh Medical Center (UPMC) Presbyterian Hospital, UPMC Montefiore Hospital, Kaufmann Building, and/or Falk Clinic. Subjects will need to fast a minimum of 2 hours prior to these visits. These procedures will be completed over 2-3 days.

- Cardiopulmonary exercise test (CPET): Incremental exercise testing (IET), a practice constant work rate (CWRP) test, and baseline constant workrate (CWRB) test, Spirometry- Forced vital capacity (FVC) maneuver only
- Accelerometer activity monitor to be worn for about 7-10 days
- Completion of The Kansas City Cardiomyopathy Questionnaire (KCCQ), 36-Item Short Form Health Survey (SF-36), and Pulmonary Arterial Hypertension Symptoms and Impact Questionnaire (PAH-SYMPACT).

A physical exam with NYHA functional class assessment may be performed and this will be completed on a case by case basis at the discretion of the study physician.

Subjects who report using PDE-5 inhibitor medications and do not need a screening RHC will be asked to hold the medication 5 days before the initial study drug or placebo dose and throughout the study. Patients who are fatigued or short of breath after stopping PDE5i, if specifically done for the study, will be evaluated and if it is felt to be related to stopping PDE5i will be restarted and they will continue in the trial with monitoring as per the trial.

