## 2.3.6. Schedule of Assessments

The table below summarizes the protocol procedures that will be performed throughout the study trial TABLE 1

TABLE 1										
Study Phase	Screening	Baseline	Weekly Phone Call +/- 7 days	Weeks 4 and 8 (per Pl only) +/- 7 days	Week 10 +/-14 days	Cross- over Visit	Weekly Phone Call +/- 7 days	Weeks 4 and 8 (per Pl only) +/- 7 days	End of Treatment (EOT)	Follow-up Period Phone Call
Informed Consent	X									
I/E Criteria	X									
Medical History &	Х									
Demographics	v			V	v	V		V	V	
Physical Exam	X	Х		X	X	X		X	X	
Vital Signs & Body Weight		Χ								
Oxygen Saturation	X			X	X	X		X	X	
Blood Samples: fasting glucose, CMP, hemoglo bin A1C, fasting lipid profile, PT/PTT, complete blood count, platelet and differential, research labs	X				х	X			х	
α NTproBNP blood test	Х			Х	Х	Х		Х	Х	
Urine Pregnancy test (if applicable)	X				X	X			x	
NYHA functional class assessment	Х			X	X	X		х	X	
α 6 minute walk test (6MWT)	Х			Х	Х	Х		Х	Х	
Echocardiogram	X∞				Х				х	
Spirometry lung	X.	Х							Α	
function test										
Incremental exercise testing (IET)		Х								
Practice Constant Work Rate (CWR P )		Х								
Constant Work Rate (CWR) test		Х			Х	Х			Х	
(RHC): RA, RV, PA, PCWP, CO/CI Resting hemodynamics and (sub-maximal exercise at Week 10 and EOT only)	Χ †				х				Х	
Micromanometry     (optional)	X				X				X	
Accelerometer		Х			Х	Х			Х	
л IVGTT					Х				X	
MetHgb levels via co-	Х	Х		Х	Х	Х		Х	X	
oximetry		v								
Randomization Dispense and study		X		X	Х	Х		X	If patient wants to	
drug administration		^							continue open label	
Study drug compliancy assessment				Х	Х			Х	X	
Dispense subject diary		Х		Х	Х	Х		Х	Х	
α KCCQ, SF-36 and PAH-SYMPACT questionnaires		Х			Х	Х			Х	
AE Assessment			Х	Х	Х	Х	Х	Х	х	Х
Review of concomitant medications	Х		X	X	X	X	X	X	x	
Interval History Assessment			Х	Х	Х	Х	Х	Х	Х	Х

- Sponsor: [name]
- ∞ If subject has had an echocardiogram within the past year, we may not obtain during screening.
- Spirometry lung function test may not be needed at baseline visit if results are available within 6 months from enrollment.
- ↑ A screening RHC may not be performed if a RHC was completed within 12 months from enrollment per PI discretion.
- 3 Micromanometry is optional and completed during RHC.
- n Insulin-dependent diabetics will not receive the IVGTT.

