## 2.8 STATISTICAL ANALYSIS

#### 2.8.1 Sample Size and Power

**Sample size:** Prior study has indicated that oral nitrate reduces baseline mean PAP -7 (SD = 4) mm Hg vs. -3 (4) mmHg in placebo group. A sample size of 12 in each group provides 88%

power to detect this difference. This sample size will provide 80% power to detect -10 (6) vs. -5 (6) decrease in post-exercise mPAP in treatment and placebo group, respectively.

**Statistical analysis:** Pre-randomization characteristics of two groups will be presented using the median (interquartile range) or frequency tables at each study sequence. The difference of mPAP during submaximal exercise as compared between placebo and nitrite at 10 weeks (i.e. the week 10 RHC of placebo vs week 10 RHC of nitrite) using the parametric PK-cross analysis (i.e. an ANOVA which determines the sequence, period, carryover, and treatment effects). Post-exercise values of before and after crossover will be compared between two groups using similar approach. For secondary outcomes, we will compare the difference of baseline and follow-up value and compare these differences with a parametric test. Alternatively a nonparametric test will be used for these comparisons. For both primary and secondary outcomes, treatment effect in each sequence as well as mean (SD) total treatment effect and corresponding P values will be reported.

We will also test the effect of treatment on pre-exercise mPAP and secondary outcomes using mixed effect models. In all analysis, missing data will be imputed and sensitivity analysis with imputed data will be performed. All analyses will be performed by ITT approach.

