#### 3.3 EXCLUSION CRITERIA

Subjects meeting any of the exclusion criteria at baseline will be excluded from participating in study.

- Age less than 18 years
- SBP > 170 or < 110 mmHg
- DBP > 95 or < 60 mmHg
- Hemoglobin A1C > 10
- Positive urine pregnancy test or breastfeeding
- Ejection Fraction < 40%
- Dementia
- End-stage malignancy
- Major cardiovascular event or procedure within 6 weeks prior to enrollment
- Severe valvular disease
- Known chronic psychiatric or medical conditions that may increase the risk associated with study participation in the judgement of the investigator would make the subject inappropriate for entry into this study
- Smoker
- Hemoglobin < 9 g/dL
- Serum creatinine > 3.0 mg/dL
- Recent (<3 months) addition or change in dosing of hormonal contraceptive medications (OCP, IUD, DepoProvera)
- Receipt of an investigational product or device, or participation in a drug research study within a period of 15 days;
- RHC < 2 weeks from study screening RHC unless clinically indicated

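### Resting RHC and echo outcomes are to be analysed as change from baseline, but that baseline may be a clinical test up to a year old and neither test is repeated at cross-over; compare the two end-of-period values instead

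*Combined protocol and SAP*

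**What the plan says.** On the age of the baseline tests:

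- RHC: "If a RHC has been completed within 12 months from enrollment, test results may be considered for baseline measurements" (section 2.3, repeated in 2.3.1). The footnote to Table 1 adds: "A screening RHC may not be performed if a RHC was completed within 12 months from enrollment per PI discretion". Section 2.4.8, by contrast, describes the screening RHC as serving eligibility.
- Echo: "if subject has had an echocardiogram within the past year we may not obtain during screening" (2.3.1, and a Table 1 footnote). No other pre-treatment echo is scheduled.

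On timing: Table 1 places RHC and echo at screening, Week 10 and end of treatment (EOT). The cross-over visit in 2.3.3 repeats the walk test, constant work rate test, accelerometer, bloods and questionnaires, but neither RHC nor echo.

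On analysis (2.8.1), for secondary outcomes: "we will compare the difference of baseline and follow-up value and compare these differences with a parametric test". A nonparametric test is the alternative, and mixed effect models are planned as well. The text does not say whether the test is paired, which value is the period-2 baseline, or what role baseline has in the mixed models. The secondary endpoints in 2.6.2 include RHC haemodynamics and Doppler echo.

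On background treatment: section 2.3.1 asks PDE-5 inhibitor users to hold the drug for 5 days before the screening RHC. Section 2.3.2 says users who "do not need a screening RHC will be asked to hold the medication 5 days before the initial study drug or placebo dose".

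**The concern.** A change score needs a baseline that represents the patient just before treatment. For resting haemodynamics and echo, the only pre-treatment value may come from a clinical test up to a year before enrollment. Counting from that test, follow-up can be about 52 + 10 = 62 weeks later at Week 10 and 52 + 22 = 74 weeks later at EOT. Whatever changed in between enters the change score.

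Background treatment can differ as well. A patient who enters on an old RHC is asked to stop a PDE-5 inhibitor only before the first dose, so that RHC may have been recorded on the drug. A patient who has a screening RHC is asked to stop before it. The reported mean change on each treatment would then mix two kinds of baseline.

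The more basic gap is in period 2. With no RHC or echo after washout, the change-score rule has no sound period-2 baseline for these outcomes. The analyst must either reuse the pre-trial value or take Week 10, which was measured on the first treatment. At stake are the secondary resting pressure, resistance, compliance and echo results.

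**Working it through.** **Inputs.** From 2.8.1: mean resting change of -7 versus -3 mmHg (difference 4), SD 4, 12 in each group, 88% power. Assumed: two-sided 5% level (none is stated), 24 patients with both periods (12 per sequence), and a drift SD between the old test and the true pre-treatment value of 3, 4 or 6 mmHg. The documents give no drift SD.

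**The plan's own figure.** A paired t-test with n = 12, difference 4 and SD of the within-patient difference 4 gives 88.3%, matching the stated 88%. A two-sample t-test with 12 per group gives 64.9%. The stated power therefore fits a within-patient comparison.

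**Paired use of one shared baseline.** Let B be the old baseline and Y_N and Y_P the end-of-period values. Then (Y_N - B) - (Y_P - B) = Y_N - Y_P. B drops out, so its age is irrelevant. In simulation, paired power stayed at about 91% at every drift SD (SD of each change 4, no other within-patient correlation).

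**Unpaired use of change scores.** A patient's drift is common to both change scores. The mean difference keeps its true standard error, sqrt(2 × 16/24) = 1.155, but the unpaired test uses sqrt(2 × (16 + d²)/24), where d is the drift SD. Power is approximately the chance that a normal variable with mean 4 and SD 1.155 exceeds 2.013 times the standard error used (2.013 is the 97.5% t point on 46 df).

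| d (mmHg) | standard error used | threshold | approximate power | simulated power |
|---|---|---|---|---|
| 0 | 1.155 | 2.32 | 93% | 92% |
| 3 | 1.443 | 2.91 | 83% | 82% |
| 4 | 1.633 | 3.29 | 73% | 73% |
| 6 | 2.082 | 4.19 | 43% | 45% |

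If only half the patients have an old baseline (assumed), the simulated values at d = 3, 4 and 6 are about 88%, 83% and 70%. The mean difference stays at -4 throughout, so this is lost power and not bias.

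*Sensitivity.* SD 4 for each change and SD 4 for the within-patient difference are both true if the two changes correlate at 0.5. Unpaired power is then about 97% with no drift, 78% at d = 4 and 43% at d = 6, while paired power stays near 99.6%.

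**Week 10 as the period-2 baseline.** Use the plan's means and assume no carryover.

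- Nitrite first: nitrite change -7; placebo change -3 - (-7) = +4; difference -11.
- Placebo first: placebo change -3; nitrite change -7 - (-3) = -4; difference -1.
- Average: (-11 - 1)/2 = -6, against a true -4, a ratio of 1.5.

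Simulation gave -5.99. A uniform shift in the period-1 baseline does not alter the average, so this bias does not depend on the age of the first test.

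**The case against.** The strongest reply is that a crossover analysis removes the problem. That is right as far as it goes: with one shared baseline and paired analysis, the old value cancels exactly. Section 2.8.1 also plans mixed effect models for pre-exercise mPAP and the secondary outcomes, and these can use within-patient information. Twelve months is an upper limit applied at the investigator's discretion, not the rule for every patient.

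A reader might infer more than the documents support:

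- *That a year of drift biases the nitrite-placebo comparison.* It does not in complete pairs. It affects the change reported for each treatment and, in an unpaired test, the precision.
- *That the plan specifies an unpaired test.* It says only that the test is parametric, with a nonparametric alternative. The power losses above are conditional on the unpaired reading.
- *That Week 10 is the period-2 baseline.* No section says so. The 1.5-fold figure shows what that choice would do.
- *That the primary endpoint suffers.* Section 2.6.1 compares the two end-of-period exercise RHCs and uses no baseline.
- *That reused laboratory values are equally stale.* Their window is 30 days before screening, the bloods are redrawn at cross-over, and 2.4.6 sends NT-proBNP to the core laboratory.
- *That patients could enter on an ejection fraction predating a cardiac event.* This is a separate eligibility matter and speculative: the echo may still be repeated, history and examination are required, and a study physician confirms eligibility.

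What remains is that the stated change-score rule does not fit outcomes with no post-washout measurement, and the text does not rule out either harmful reading.

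**Conclusion.** The point holds in limited form. For resting RHC haemodynamics and Doppler echo, the change-from-baseline rule in 2.8.1 rests on a value that may be up to a year old and has no sound counterpart in period 2. That baseline cannot improve the treatment contrast. It cancels in a paired analysis, lowers power from about 92% to between 82% and 45% in an unpaired one (drift SD 3 to 6 mmHg in every patient, less if only some are affected), and is avoided by taking Week 10 only at the price of a 1.5-fold overestimate. It also makes the per-treatment change from baseline hard to interpret, partly because the PDE-5 inhibitor state may differ by entry route.

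The drift SDs, the 24 complete pairs and the 5% level are assumptions. The primary endpoint is untouched. This is a free improvement to the secondary analyses, not a flaw that threatens the main result.

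**What to change.** - **Section 2.8.1:** analyse resting RHC and echo secondary outcomes as the within-patient contrast of the two end-of-period values (Week 10 versus EOT), in the same crossover model as the primary endpoint. State that no Week 10 value serves as a period-2 baseline and that any change from baseline for these outcomes is descriptive.
- **Sections 2.3 and 2.3.1 and the Table 1 footnotes:** limit historical RHC and echo results to eligibility and description, in line with the purpose given for the screening RHC in 2.4.8.
- **Sections 2.3.1 and 2.3.2:** reconcile the two PDE-5 inhibitor passages, so that the background treatment at the RHC called baseline is clear for both entry routes.

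The cost is wording only. No catheterization or echo is added. The sponsor gives up change from baseline as an inferential result for these outcomes and keeps it as a descriptive display.

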#### 2.3.1. Screening Procedures

The outpatient visits will take place in various outpatient clinics and/or procedural areas throughout the University of Pittsburgh Medical Center (UPMC) Presbyterian and UPMC Montefiore Hospitals. The screening procedures will take place over 2 days if screening RHC is needed. Subjects will be asked to fast a minimum of 8 hours prior to each visit. These screening procedures will determine eligibility for the study.

- Obtain written informed consent
- Complete history and physical examination to include body weight, height
- Vital signs that include: blood pressure (BP), pulse, respirations, and pulse oximetry
- Obtain waist measurement
- Review of concomitant medications
- NYHA functional class assessment
- 6 minute walk test (6MWT) and Borg scale
- MetHb level via co-oximetry (pre single dose and 30 minutes post single dose). Due
  to unknown reasons the co-oximeter device may not be able to read metHb levels. In
  that event, a blood sample will be collected to test metHb levels at approximately 3045 minutes after the 40mg dose.
- Blood samples: fasting glucose, comprehensive metabolic panel, hemoglobin A1C, fasting lipid profile, PT/PTT, complete blood count, platelet and differential, NT-proBNP. The total volume of blood drawn is approximately 1 ½ tablespoons (20 mL). If any of the above tests were done within 30 days before the screening visit, they may or may not be repeated for research purposes.
- Urine pregnancy test for women of childbearing potential
- Echocardiogram (if subject has had an echocardiogram within the past year we may not obtain during screening)
- Right heart catheterization (with optional micromanometry), research blood samples
  for plasma nitrite concentrations, red cell iron-nitrosyl-hemoglobin and platelet studies,
  and open label 40mg oral nitrite dosing with methemoglobin level. Research blood
  samples will be collected prior to taking the 40mg oral nitrite and approximately
  30-45 minutes post-dose.
- A RHC may be performed to determine the PH-HFpEF eligibility criteria. The RHC will be conducted at UPMC Presbyterian Hospital, 3rd FL Catheterization Laboratory. The RHC hemodynamic measurement parameters for PH-HFpEF eligibility are as follows: mPAP ≥ 25 mm Hg; PCWP ≥15 and TPG ≥ 12. If a RHC has been completed within 12 months from enrollment, test results may be considered for baseline measurements. The total volume of blood drawn is approximately 1 ¾ tablespoons

(26mL). Subjects who report using PDE-5 inhibitor medications will be asked to hold the medication 5 days before the screening RHC and throughout the study.

#### 2.3.2. Baseline Procedures

After eligibility has been confirmed, the following procedures will take place in various outpatient clinics and/or procedural areas throughout the University of Pittsburgh Medical Center (UPMC) Presbyterian Hospital, UPMC Montefiore Hospital, Kaufmann Building, and/or Falk Clinic. Subjects will need to fast a minimum of 2 hours prior to these visits. These procedures will be completed over 2-3 days.

- Cardiopulmonary exercise test (CPET): Incremental exercise testing (IET), a practice constant work rate (CWRP) test, and baseline constant workrate (CWRB) test, Spirometry- Forced vital capacity (FVC) maneuver only
- Accelerometer activity monitor to be worn for about 7-10 days
- Completion of The Kansas City Cardiomyopathy Questionnaire (KCCQ), 36-Item Short Form Health Survey (SF-36), and Pulmonary Arterial Hypertension Symptoms and Impact Questionnaire (PAH-SYMPACT).

A physical exam with NYHA functional class assessment may be performed and this will be completed on a case by case basis at the discretion of the study physician.

Subjects who report using PDE-5 inhibitor medications and do not need a screening RHC will be asked to hold the medication 5 days before the initial study drug or placebo dose and throughout the study. Patients who are fatigued or short of breath after stopping PDE5i, if specifically done for the study, will be evaluated and if it is felt to be related to stopping PDE5i will be restarted and they will continue in the trial with monitoring as per the trial.

## **Randomization**

Randomization to study drug verses placebo will occur upon completion of all screening and baseline procedures and confirmation by a study physician that subjects have met all eligibility criteria. Randomization of sequence of nitrite-placebo versus placebo-nitrite followed by cross-over to the alternative treatment in a 1:1 ratio according to a computer generated pseudo-random code.

Subjects will self-administer their first dose of study medication or placebo under supervision of the physician investigator or the primary study coordinator after eligibility has been confirmed. Each patient will have their vital signs and methemoglobin measured before taking the study medication and approximately 30-45 minutes after taking their first dose.

Subjects will also be dispensed their study medication for home use including a medication administration diary. Subjects will return the previously dispensed study medication and diary at every study visit thereafter, and medication compliance will be assessed.

